The plan for handling of missing data is described in e-Appendix 1.

Ethics and Dissemination

Critically ill patients undergoing tracheal intubation are at significant risk for morbidity and mortality from the underlying illness. Most patients undergoing tracheal intubation in routine clinical care receive preoxygenation with either noninvasive ventilation or an oxygen mask. Any benefits or risks of these two approaches are experienced by patients undergoing tracheal intubation in clinical care, outside the context of research. As a requirement for enrollment in PREOXI, the patient's treating clinician must determine that either preoxygenation with noninvasive ventilation or preoxygenation with an oxygen mask would be a safe and reasonable approach for the patient. Otherwise, the patient is excluded. Therefore, making the decision between the two approaches randomly in the context of a trial, rather than by a clinician who thinks either approach is safe, is expected to pose no more than minimal additional risk.

Obtaining informed consent from potential study participants or their legally authorized representatives would be impracticable. Most critically ill patients undergoing emergency tracheal intubation lack decisional capacity because of the critical illness and surrogate decision-makers frequently are unavailable. Further, emergency tracheal intubation is a time-sensitive procedure with only minutes between the decision to intubate and the completion of the procedure. Meaningful informed consent could not be executed in this brief window.

Because the study involves minimal incremental risk, the study would not adversely affect the welfare or privacy rights of the participant, and because obtaining informed consent would be impracticable, a waiver of informed consent was requested from and approved by the single institutional review board at Vanderbilt University Medical Center (Identifier: 211271). Conduct of this trial with waiver of informed consent is consistent with previous randomized trials comparing alternative approaches to tracheal intubation in widespread clinical use.^{2,15-17,22,23} This approach was approved secondarily by the US Department of Defense Health Agency Human Research Protection Office. Institutional review boards at participating sites reviewed the protocol, addressed any local contextual factors, and ceded responsibility for ethics approval and study oversight to the single institutional review board.

Discussion

Herein, we report the rationale, design, and analysis plan for PREOXI, a 1,300-patient randomized trial of preoxygenation with noninvasive ventilation vs preoxygenation with oxygen mask among critically ill adults undergoing emergency tracheal intubation in the ED or ICU. Several important trial design elements bear additional consideration.

We selected hypoxemia (as a binary variable), rather than lowest oxygen saturation (a continuous variable), as the primary outcome for the trial for several reasons. First, experiencing hypoxemia in the range associated with an increased risk of adverse clinical outcomes (eg, cardiac arrest) may be more clinically relevant than changes in oxygen saturation within the normal range. For example, a change in oxygen saturation of 5 percentage points from 87% to 82% may be associated more closely with adverse outcomes than a change in oxygen saturation of 10 percentage points from 100% to 90%. Second, values for oxygen saturation are right-censored because oxygen saturation reaches 100% with a PaO_2 of approximately 100 mm Hg, but patients may have a higher PaO_2 after preoxygenation. The approach of analyzing hypoxemia as a binary variable, rather than lowest oxygen saturation, has been used by many prior trials and has been endorsed by airway experts.²⁴⁻²⁹

We selected an oxygen saturation of < 85% as the threshold for the primary outcome based on several physiologic and procedural factors. First, an oxygen saturation of 85% corresponds with the inflection point on the oxyhemoglobin dissociation curve, at which

further decrements in arterial oxygen concentrations result in rapid and critical desaturation.⁹ Second, an oxygen saturation of < 85% has been associated with an increased risk of cardiac arrest during tracheal intubation³⁰ and may be associated with increased mortality.⁵

Another trial design element that warrants consideration is the decision to allow the use of either a non-rebreather mask or a bag-mask device to provide preoxygenation in the oxygen mask group. Both devices can be used to provide supplemental oxygen without positive-pressure ventilation, but differ in some respects. A non-rebreather mask uses a loose-fitting interface and requires no provider involvement, whereas a bag-mask device requires a provider to hold the mask in place and can provide a tight mask seal. A bag-mask device also can be used to provide positive-pressure ventilation, which in the oxygen mask group of the current trial was allowed only after induction of anesthesia. Although these differences theoretically could affect preoxygenation, available evidence suggests that the two devices perform similarly.³¹ Any theoretical difference in preoxygenation between two devices providing oxygen is likely to be much smaller than the difference between these devices, which provide supplemental oxygen alone, and devices that provide both supplemental oxygen and positive-pressure ventilation (ie, the noninvasive ventilation group in PREOXI). Allowing both types of oxygen masks routinely used in clinical care also increases the generalizability of trial results.

The use of positive-pressure ventilation after induction of anesthesia (the end of preoxygenation) is allowed in both trial groups. Evidence from a prior randomized trial conducted among patients in the ICU suggests that bag-mask ventilation between induction and laryngoscopy reduces the risk of hypoxemia.² However, the safety and efficacy of bag-mask ventilation has not been evaluated among patients in the ED. Some experts have advocated avoiding bag-mask ventilation among patients in the ED who are less likely to have fasted than patients in the ICU and therefore may be at higher risk of aspiration.³² Because PREOXI enrolls patients in both the ED and ICU and focuses on preoxygenation and not management between induction and laryngoscopy, trial protocol allows bag-mask ventilation after induction of anesthesia, but does not mandate it.

The final design consideration is the administration of supplemental oxygen via standard nasal cannula and high-flow nasal cannula. Because oxygen facemasks

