5.3 Enrollment and Randomization

All patients requiring emergency tracheal intubation in a participating ED or ICU will be screened for eligibility for the PREOXI trial using the eligibility criteria in Section 3. Patients who do not meet inclusion criteria will be considered ‘ineligible’. Patients who meet inclusion criteria but also meet at least one exclusion criterion will be considered ‘excluded.’ For patients who are excluded, the reason for exclusion will be recorded. For patients who do meet eligibility criteria but are not enrolled, the reason will be recorded.

At enrollment, patients will be randomized in a 1:1 ratio to preoxygenation with non-invasive positive pressure ventilation or preoxygenation with facemask oxygen using randomly permuted blocks of variable size. The randomization will be stratified by study site (i.e., each participating ED or ICU will comprise a different stratum). The study group assignment will be placed in opaque randomization envelopes, which will be located within participating units. Study group assignment will remain concealed to study personnel and treating clinicians until after the decision has been made to enroll the patient in the study.

To facilitate rapid enrollment during this time-sensitive procedure, sequentially numbered randomization envelopes will be located adjacent to the equipment required for emergency

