settings, detecting a 6% absolute decrease in the incidence of hypoxemia with 85% power at a two-sided alpha level of 0.05 would require enrollment of 1,264 patients (632 per group). Anticipating missing data for up to 3% of patients, we will plan to enroll a total of 1,300 patients (650 per group). This sample size calculation was performed in PS version 3.1.2.

11.2 Statistical Analysis:

Prior to the conclusion of enrollment, we will make publicly available a complete, final statistical analysis plan. Analyses conducted in accordance with the statistical analysis plan will be identified as *a priori*. Any additional analyses requested by the investigators or reviewers will be identified as *post hoc*.

11.2.1 Primary Analysis:

The primary analysis will be an unadjusted, intention-to-treat comparison of patients randomized to preoxygenation with non-invasive positive pressure ventilation versus patients randomized to preoxygenation with facemask oxygen with regard to the primary outcome. The difference between the two study groups will be compared using a Chi-squared test.

11.2.2 Secondary Analysis:

We will perform intention-to-treat comparisons of secondary, exploratory, and safety outcomes. Continuous outcomes will be compared with Wilcoxon Rank Sum test and categorical variables with the Chi-squared test. Data on patient characteristics will be summarized as number and proportion for categorical variables and as median and interquartile range for continuous variables.

We will also perform an adjusted comparison of the primary outcome between groups using a generalized linear mixed effects model including a random effect for site and fixed effects for group assignment and the following pre-specified baseline variables:

1. Age;
2. Sex;
3. Race and Ethnicity;
4. BMI;
5. Location at enrollment (ED or ICU)
6. Highest fraction of inspired oxygen in the hour prior to initiation of preoxygenation;
7. APACHEII score; and
8. Indication for intubation (hypoxic respiratory failure: Yes vs No)
9. Operator experience (number of previous intubations the operator has performed)

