11.3 Interim Analysis

The DSMB will conduct a single interim analysis for efficacy and safety at the anticipated halfway point of the trial, after enrollment of 650 patients. The pre-specified stopping boundary for efficacy will be a P value < 0.001 for the difference between group in the primary outcome using a Chi-square test. This conservative Haybittle–Peto boundary will allow the final analysis to be performed using an unchanged level of significance (two-sided P value < 0.05).

Finally, after the interim analysis, the DSMB will evaluate the rate of the primary outcome in the facemask group. If the incidence of the primary outcome in the facemask group differs from the original estimate, the DSMB may suggest an increase sample size that would maintain the pre-planned statistical power to detect the pre-planned relative risk difference in the primary outcome between groups.

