STUDY DESIGN AND METHODS: The Pragmatic Trial Examining Oxygenation Prior to Intubation (PREOXI) is a prospective, multicenter, nonmasked randomized comparative effectiveness trial being conducted in seven EDs and 17 ICUs across the United States. The trial compares preoxygenation with noninvasive ventilation vs oxygen mask among 1,300 critically ill adults undergoing emergency tracheal intubation. Eligible patients are randomized in a 1:1 ratio to receive either noninvasive ventilation or an oxygen mask before induction. The primary outcome is the incidence of hypoxemia, defined as a peripheral oxygen saturation of < 85% between induction and 2 min after intubation. The secondary outcome is the lowest oxygen saturation between induction and 2 min after intubation. Enrollment began on March 10, 2022, and is expected to conclude in 2023.

INTERPRETATION: The PREOXI investigation will provide important data on the comparative effectiveness of preoxygenation with noninvasive ventilation vs oxygen mask for the prevention of hypoxemia during emergency tracheal intubation. Specifying the protocol and statistical analysis plan before the conclusion of enrollment increases the rigor, reproducibility, and interpretability of the trial.

TRIAL REGISTRY: ClinicalTrials.gov; No.: NCT05267652; URL: www.clinicaltrials.gov

CHEST Critical Care 2023; 1(2):100014

KEY WORDS: critical illness; endotracheal intubation; noninvasive positive-pressure ventilation; oxygen; respiratory failure

Take-home Points

Study Question: Does preoxygenation with noninvasive ventilation prevent hypoxemia during tracheal intubation of critically ill adults compared with pre-oxygenation with an oxygen mask?

Results: This article describes the protocol and statistical analysis plan for the Pragmatic Trial Examining Oxygenation Prior to Intubation investigation of preoxygenation with noninvasive ventilation vs with oxygen mask.

Interpretation: Prespecifying the full statistical analysis plan before completion of enrollment increases rigor, reproducibility, and transparency of the trial results.

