Exploratory clinical	28-d in-hospital mortality.
	Ventilator-free days to 28 d.
	ICU-free days to 28 d.

Sample Size Estimation

The current trial is designed to detect a 6% absolute difference between groups in the incidence of hypoxemia, a difference that is similar to or smaller than the difference considered to be clinically meaningful in the design of prior trials of oxygenation strategies during tracheal intubation.^{2,15} Assuming an incidence of hypoxemia of 17% in the oxygen mask group based on data from two recently completed trials by this network in similar ED and ICU settings, detecting a 6% absolute decrease in the incidence of hypoxemia with 85% power at a two-sided α level of .05 would require enrollment of 1,264 patients (632 per group).^{16,17} Anticipating missing data for up to 3% of patients, we plan to enroll a maximum of 1,300 total patients (650 per group). This

sample size calculation was performed in PS version 3.1.2 software (Vanderbilt University Medical Center).

Data and Safety Monitoring Board and Interim Analysis

The data and safety monitoring board and interim analysis are described in [e-Appendix 1](#).

Statistical Analysis Principles

Analyses will be conducted following reproducible research principles using R software (R Foundation for Statistical Computing). Categorical variables will be presented as number and percentage and will be compared between groups using a χ^2 test. Continuous variables will be presented as mean \pm SD or median

(interquartile range) and will be compared between groups using a Wilcoxon rank-sum test. We will present absolute between-group differences with associated 95% CIs. A two-sided P value of $< .05$ will define a statistically significant between-group difference in the primary outcome. With a single primary outcome, no adjustment for multiplicity will be made. For secondary, safety, and exploratory analyses, emphasis will be placed on the magnitude of differences between groups with 95% CIs, rather than statistical significance.

Main Analysis of the Primary Outcome

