The main analysis will be an unadjusted intention-to-treat comparison of the primary outcome of hypoxemia between patients randomized to the noninvasive ventilation group vs patients randomized to the oxygen mask group using a χ^2 test. The absolute difference in proportions, associated 95% CI, and a P value for the comparison will be presented. The primary analysis will be conducted among patients for whom the primary outcome is available without imputation of missing data. Planned tables of baseline characteristics, procedural characteristics, and outcomes are presented in e-Tables 2 and 3.

Additional Analyses of the Primary Outcome

Multivariable Analysis: To account for relevant baseline covariates, we will fit a generalized linear mixed effects model using a logit link function with the primary outcome as the dependent variable, study site as a random effect, and fixed effects of study group and the following prespecified baseline covariates: age, sex, race and ethnicity, BMI, location at enrollment (ED or ICU), highest FIO_2 1 h before initiation of preoxygenation, Acute Physiology and Chronic Health Evaluation II score,¹⁸ indication for intubation (hypoxemic respiratory failure: yes vs no), and operator experience (number of previous intubations the operator has performed). All continuous variables will be modelled assuming a nonlinear relationship to the outcome using restricted cubic splines with between 3 and 5 knots.

Effect Modification: We will examine whether prespecified baseline variables modify the effect of study group assignment on the primary outcome using a formal test of statistical interaction in a logistic regression model with the primary outcome as the dependent variable and independent variables of study group, the proposed effect modifier, and the interaction between the two. For categorical variables, we will present the OR and 95% CIs within each prespecified subgroup. Continuous

variables will not be dichotomized for analysis of effect modification, but may be dichotomized for data presentation. In accordance with the Instrument for Assessing the Credibility of Effect Modification Analyses recommendations, we have prespecified the following baseline variables as potential effect modifiers and hypothesized the direction of effect modification for each.

Patient Location (ED vs ICU): We hypothesize that patient location will not modify the effect of study group assignment on the primary outcome.

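### The primary chi-square and its confidence interval ignore the 24 randomisation strata: a small loss of efficiency, not a validity error

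*Combined protocol and SAP*

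**What the plan says.** Protocol v1.1, section 5.3 (same wording in v1.0), defines the strata: "The randomization will be stratified by study site (i.e., each participating ED or ICU will comprise a different stratum". The abstract of the published SAP gives their number: "randomized comparative effectiveness trial being conducted in seven EDs and 17 ICUs across the United States", that is 7 + 17 = 24.

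The primary analysis does not use them. Protocol section 11.2.1 says "The difference between the two study groups will be compared using a Chi-squared test", and the published SAP (Main Analysis of the Primary Outcome) says "The main analysis will be an unadjusted intention-to-treat comparison of the primary outcome of hypoxemia between patients randomized" to each group. The headline estimate is absolute: "The absolute difference in proportions, associated 95% CI, and a P value for the comparison will be presented". The interim boundary in protocol section 11.3 is a P value "for the difference between group in the primary outcome using a Chi-square test".

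Site enters one planned additional analysis of the primary outcome (published SAP, Multivariable Analysis), a "generalized linear mixed effects model using a logit link function with the primary outcome as the dependent variable, study site as a random effect", with nine baseline covariates. The Statistical Analysis Principles say "We will present absolute between-group differences with associated 95% CIs", but nothing explains how an absolute difference would come from that model, and no site-stratified risk difference is planned. The SAP names R and a chi-square test without saying whether the test is continuity-corrected.

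**The concern.** Permuted blocks within unit keep the arms balanced in every ED and ICU, so differences in risk between units cannot add to the variance of the treatment comparison. The pooled 2x2 table still counts those differences in its standard error. When units differ, the interval is wider than the design warrants and the test rejects a true null less often than 5%.

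Only efficiency is at stake: a slightly wider interval on the headline absolute difference and a little lost power. The planned mixed model does not fill the gap. It is secondary, adjusts for much more than site, and reports on the odds-ratio scale.

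**Working it through.** **1. Reproduce the plan's sample size.** Inputs (published SAP, Sample Size Estimation): 17% vs 11%, two-sided alpha 0.05, power 85%, so z = 1.960 and 1.036, and the mean risk is 0.14.

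- Uncorrected: n = [1.960 x sqrt(2 x 0.14 x 0.86) + 1.036 x sqrt(0.17 x 0.83 + 0.11 x 0.89)]^2 / 0.06^2 = (0.9618 + 0.5067)^2 / 0.0036 = 599.0 per group.
- Continuity-corrected: n' = (n/4) x [1 + sqrt(1 + 4/(0.06n))]^2 = (599.0/4) x (1 + 1.0542)^2 = 631.9 per group.

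The stated 632 per group (1,264) is therefore the corrected figure. Without correction it would be about 1,198.

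**2. Power at the planned analysed number.** 1,300 x 0.97 = 1,261, or about 630 per group. Power is 86.7% by formula (86.9% exact) uncorrected and 84.9% (85.1% exact) corrected. Exact type I error at 17% is 4.98% and 4.19%.

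**3. Why pooling is conservative.** Let p_k be the risk in unit k. Under the null the true variance of the difference is proportional to E[p_k(1 - p_k)], while the pooled test uses 0.17 x 0.83. With k the ratio of the first to the second, true type I error is 2[1 - Phi(1.960/sqrt(k))]. The documents give no between-unit variation, so the SD of unit log-odds is an assumption. At SD 0.5, k = 0.9655, 1.960/0.9826 = 1.995, and type I error is 4.6%. At SD 0 / 0.3 / 0.5 / 0.8 it is 5.0 / 4.9 / 4.6 / 4.1%.

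**4. Simulation.** 20,000 trials per scenario: 24 units of unequal size, blocks of 2/4/6 within unit, 1,300 enrolled, 3% missing at random, normal unit log-odds, marginal risks 17% and 11% (17% in both arms under the null). Block sizes, unit sizes and a Wald interval for the pooled difference are assumptions, because the plan does not give them. For unit k with x1, x0 events among n1, n0 patients and m = n1 + n0:

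- Mantel-Haenszel risk difference: RD = sum[(x1 n0 - x0 n1)/m] / sum[n1 n0/m].
- Sato variance: (RD x sum P + sum Q) / (sum[n1 n0/m])^2, where P = [n1^2 x0 - n0^2 x1 + n1 n0 (n0 - n1)/2]/m^2 and Q = [x1(n0 - x0) + x0(n1 - x1)]/(2m).

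| SD of unit log-odds | 0 | 0.3 | 0.5 | 0.8 |
|---|---|---|---|---|
| 95% of units, centred on 17% | 17% | 10-27% | 7-35% | 4-50% |
| Power, chi-square uncorrected | 87.2% | 87.2% | 87.4% | 87.2% |
| Power, CMH | 87.2% | 87.4% | 87.8% | 88.7% |
| Paired gain (points; SE 0.06-0.09) | 0.0 | 0.1 | 0.4 | 1.5 |
| Half-width, pooled (points) | 3.81 | 3.81 | 3.81 | 3.79 |
| Half-width, Mantel-Haenszel, Sato | 3.82 | 3.79 | 3.76 | 3.67 |
| Pooled interval wider by | 0% | 0.4% | 1.3% | 3.4% |
| Type I error, chi-square (SE 0.15) | 5.0% | 5.0% | 4.6% | 4.0% |
| Type I error, CMH | 4.9% | 5.1% | 5.0% | 4.7% |
| Power, chi-square corrected | 85.3% | 85.3% | 85.4% | 85.6% |

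The point estimate moves by 0.06 to 0.10 points on average. A second simulation, with 1,264 patients in equal units or in units of 7 to 170 patients, gave gains of about 0, 0.2, 0.5 and 1.3 points, and 2.1 to 2.2 at SD 1.0.

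**5. Coverage and interim.** Null coverage of the Sato interval is 95.1 / 94.8 / 95.0 / 95.2%; with a large-stratum variance it is 94.7 / 94.4 / 94.5 / 94.8%. At 650 enrolled, the chance of P < 0.001 under the design effect goes from 12.8 to 12.5% (SD 0), 12.5 to 12.7%, 12.6 to 13.2% and 12.3 to 14.5% (SD 0.8) when CMH replaces the uncorrected chi-square (paired SE 0.07-0.12).

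**The case against.** An unadjusted pre-specified chi-square is legitimate, has been the primary test since protocol v1.0, keeps type I error at or below about 5% and meets its planned power. The benefit of stratifying depends on an assumed spread. It exceeds one point only at SD 0.8 or above, where 95% of units would span 4 to 50% risk, which nothing in the documents supports. Site already appears in a planned model. All of this stands, and it limits the point to a modest recommendation.

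Two further objections stand in part. First, with a constant odds ratio the risk difference varies by unit. Against a fixed 6-point population value, both intervals under-cover at SD 0.8, the stratified one more (92.7% vs 93.6%). The stratified estimate should therefore be described as referring to the participating units; for that target its coverage is 94.8 to 95.1%. The no-cost claim concerns the final analysis when units do not differ, and there it holds. At the interim with SD 0 there is a loss of about 0.3 points.

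Second, the SAP revision sequence puts the last enrolment on October 14, 2023, after publication of the SAP. Changing the primary test may no longer be defensible, and the recommendation depends on that timing.

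**Conclusion.** The point holds. The design is stratified by 24 units, while the primary test, its interval and the interim test are not. The consequence is mild conservatism: an interval 0 to 3.4% wider than needed and 0 to 1.5 points of power forgone over an assumed SD of 0 to 0.8. Validity is unaffected, and a reader's conclusion would change only if P fell very close to 0.05.

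The unstated continuity correction matters at least as much. Subtracting the rounded powers in the table gives 1.6 to 2.0 points, and the correction lowers exact type I error from 4.98% to 4.19% even when units do not differ.

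The size of the stratification gain rests on the assumed unit variation, blocks and unit sizes. Its direction does not.

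**What to change.** **If no outcome data by group have been seen:** by dated SAP amendment, make the primary test CMH stratified by randomising unit, without continuity correction. Report the Mantel-Haenszel risk difference with a 95% interval from the Sato variance, not a large-stratum variance. State that units with patients in one arm only drop out, that units with no events add nothing to the test, and that the estimate refers to the participating units. Keep the pooled chi-square as supportive and say whether it is continuity-corrected. Use the stratified test at the interim only if that analysis has not been done; given the enrolment date it is probably past.

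**If outcome data by group have been seen:** keep the chi-square as primary, state its correction, and add the site-stratified risk difference with its Sato interval as supportive. Protocol section 11.2 would label this addition post hoc.

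**Cost:** a few lines of R, with no new data or patients. In the simulations, one-arm units removed on average 0.3 of 1,261 patients (1.6 with very unequal units), and 1.5 to 2.7 of 24 units had no events (3.8 to 4.6 with very unequal units).
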